11. SCHEDULE OF EVALUATIONS BY VISIT

A table displaying the Schedule of Evaluations is in Appendix A. Regardless of treatment arm assigned, subjects will complete each visit in the schedule of evaluations below.

11.1. **Preoperative Visit (Up to 4 months prior to Surgery)**

Many of the screening assessments required to ensure subject eligibility are also considered the pre-operative assessments. The results of the assessments will be captured on the following Screening/Pre-operative Case Report Forms:

- SUBJECT INFORMATION / MEDICAL HISTORY
- CONCOMITANT MEDICATIONS
- PAIN MEDICATIONS
- INCLUSION/EXCLUSION CRITERIA
- KNEE SOCIETY SCORE (Surgeon portion)

The subject will complete the following function tests and questionnaires to assess pain and function as part of their preoperative assessment:

- THE KNEE INJURY AND OSTEOARTHRITIS OUTCOME SCORE (KOOS)
- KNEE SOCIETY SCORE (Subject portion)
- TIMED "GET UP AND GO"
- 8 METER WALK
- TIMED UP AND DOWN STAIRS

X-rays:

- 3 views – AP, lateral, sunrise or Merchant
- Three foot standing x-ray (full length, full weight-bearing film): AP view

11.2. **Surgery Visit (Day 0)**

The Investigator will surgically implant either the iTotal CR in compliance with the ConforMIS surgical training and Instructions for Use, or the off-the-shelf TKR per their surgical training and the manufacturer's Instructions for Use.

The site will complete the following Case Report Forms:

- SURGICAL SUMMARY
- DISCHARGE SUMMARY
- CONCOMITANT MEDICATIONS (optional)
- PAIN MEDICATIONS
- ADVERSE EVENTS (if any occur during surgery through discharge from hospital)

X-rays: None

11.3. **90 Days Follow-up Visit (\pm 14 days)**

At the 90 days follow-up visit, the Investigator or study staff will perform a post-operative knee assessment and identify any adverse events that have occurred since the subject was discharged from the hospital. The site will also collect the Uniform Billing (UB) form from their billing department if contracted with the Sponsor to participate in the Economic Sub-study.

The site will complete the following Case Report Forms:

- FOLLOW UP
- KNEE SOCIETY SCORE (Surgeon portion)

- CONCOMITANT MEDICATIONS (optional)
- PAIN MEDICATIONS
- ADVERSE EVENTS (if any)
 - REVISION FORM (if necessary)

The subject will complete the following function tests and questionnaires to assess post-operative pain and function:

- THE KNEE INJURY AND OSTEOARTHRITIS OUTCOME SCORE (KOOS)
- KNEE SOCIETY SCORE (Subject portion)

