12. SAFETY REPORTING

All Adverse Events (AEs) that are at least possibly related to the knee replacement device or procedure will be recorded by the site from surgery on the Adverse Event CRF and should be reported to Sponsor within 5 working days of site becoming aware of the event. In addition, all Serious Adverse Events (SAEs) and Unanticipated Adverse Device Effects (UADEs) must be reported to ConforMIS or designee via [contact]) or email ([contact]) as soon as possible once discovered by the site. SAEs should be reported to ConforMIS within 3 working days, and UADEs should be reported to ConforMIS within 2 working days. The Investigator and investigative site will also be responsible for required reporting to the site’s Institutional Review Board / Independent Ethics Committee (IRB/IEC) for all AEs, SAEs, and UADEs.

In the communications to ConforMIS or the IRB, include the protocol number and subject ID either in the subject of the email or the beginning of the call. ConforMIS will confirm receipt of the AE/SAE. If possible, include the AE/SAE CRF and supporting documents to ConforMIS as soon as possible.

For the purposes of this protocol, for the first 90 days following surgery, all AEs categorized as Possible, Probable or Definite in relationship to the device or procedure should be

recorded. At day 91, only those AEs categorized as Possible, Probable, or Definite in relationship to the device, as deemed by the investigator, will be recorded. Those events that are Unlikely or Not Related to the device and procedure will not be collected. Please see definitions below.

All SAEs will be recorded regardless of relationship to the device or procedure.

ConforMIS will be responsible for safety reporting as required by applicable regulatory bodies.

Adverse Event: Any untoward or unfavorable medical occurrence associated with the use of a medical product in a human patient, including any abnormal sign, symptom, or disease. Report only those AEs with Possible or above, relationship.

Definite:	Clear-cut temporal association and no other possible cause.
Probable:	Clear-cut temporal association and a potential alternative etiology are not apparent.
Possible:	Temporal association is less clear and other etiologies are also possible.
Unlikely:	Temporal association and the nature of the event is such that the study device is not likely to have had any association with the observed event (cause and effect relationship improbable but not impossible)

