3	_____ : _____ . _____	_____ : _____ . _____	Y N	0	1	2	3	4	5	6	7	8	9	10
Did the subject require a rest between the Chair and Walking activities?				Y	N									
Trial	Walking Time (mm:ss.ms)	Walking Rest Time (mm:ss.ms)	Circle Pain Level After Each Trial											
1	_____ : _____ . _____	_____ : _____ . _____	0	1	2	3	4	5	6	7	8	9	10	
2	_____ : _____ . _____	_____ : _____ . _____	0	1	2	3	4	5	6	7	8	9	10	
3	_____ : _____ . _____	_____ : _____ . _____	0	1	2	3	4	5	6	7	8	9	10	
Did the subject require a rest between the Walking and Stairs activities?				Y	N									
Trial	Stairs Time (mm:ss.ms)	Stairs Rest Time (mm:ss.ms)	Rails Used?	Circle Pain Level After Each Trial										
1	_____ : _____ . _____	_____ : _____ . _____	Y N	0	1	2	3	4	5	6	7	8	9	10
How confident were you in your ability to complete the Stairs during that trial?				Very	Somewhat	Not Very	Not At All							
Do you feel comfortable completing the Stairs a second time?				Y	N									
2	_____ : _____ . _____	_____ : _____ . _____	Y N	0	1	2	3	4	5	6	7	8	9	10
How confident were you in your ability to complete the Stairs during that trial?				Very	Somewhat	Not Very	Not At All							
Do you feel comfortable completing the Stairs a third time?				Y	N									
3	_____ : _____ . _____	_____ : _____ . _____	Y N	0	1	2	3	4	5	6	7	8	9	10
How confident were you in your ability to complete the Stairs during that trial?				Very	Somewhat	Not Very	Not At All							

Number of Steps (in staircase): _____

Observations: _____

22. APPENDIX C – U.S. Economic Sub-Study

A cost comparison between the groups will be performed. Each site will obtain the Uniform Billing (UB) forms from their billing department. These forms will have the following information for analysis:

- Length of stay
- Blood transfusions throughout the stay (number of units and type of transfusions)
- Patient discharge disposition
- Patient comorbidities
- Readmission to hospital and 30-day readmission rate
-

Additionally, in the case report forms, the following information will be collected for analysis:

- Number of trays used
- Instances of compromised tray sterility
- Procedure and device related adverse events

Primary outcome:

Economic Outcomes as measured by collected hospital data and Uniform Billing (UB) forms

Statistics:

All statistical processing will be performed using SAS® Version 9.3 or later unless otherwise stated.

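### The economic sub-study takes 30-day readmission from the enrolling site's own bills, so an admission to another hospital can be counted as no readmission

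*Combined protocol and SAP*

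**What the plan says.** Appendix C (Section 22) sets out two sources of data for the sub-study.

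- **Billing forms.** "Each site will obtain the Uniform Billing (UB) forms from their billing department". The next sentence is "These forms will have the following information for analysis", and the list under it includes "Readmission to hospital and 30-day readmission rate".
- **Case report forms.** A separate list gives the number of trays, lapses in tray sterility, and "Procedure and device related adverse events". Readmission is not on this list.

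The sub-study's primary outcome is given as "Economic Outcomes as measured by collected hospital data and Uniform Billing (UB) forms". The hospital data in that phrase are not defined.

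Section 11.3 (90-day visit) places the collection in time: "The site will also collect the Uniform Billing (UB) form from their billing department". This applies only to sites under contract for the sub-study. The same section has site staff identify adverse events since the subject left hospital.

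Section 12 counts inpatient hospitalization as a serious adverse event, with no limit to the enrolling hospital, and adds: "All SAEs will be recorded regardless of relationship to the device or procedure".

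**The concern.** A billing department can supply bills only for what its own institution charged. If a subject is admitted to a different hospital two weeks after discharge, the enrolling site has no bill for that stay, and in the billing data the subject looks the same as one who was never readmitted.

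This is misclassification, not missing data. The value appears complete and reads as no event. Appendix C's rule against imputing missing observations neither flags nor corrects it.

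A named economic outcome could therefore be too low in both arms, and a real difference between the arms would look smaller than it is. The trial already collects information that could recover at least some of these admissions, but Appendix C does not link the readmission outcome to it.

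**Working it through.** The plan states no readmission rate, no sub-study sample size and no sub-study power, so there is no figure to reproduce. The check has two parts.

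**1. Sources side by side**

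| Question | UB forms (Appendix C, Section 11.3) | SAE records (Sections 11.3 and 12) |
|---|---|---|
| Named as source for readmission? | Yes | No |
| Covers an admission to another hospital? | Not from the site's own billing department | Yes, if the site learns of it |
| Covers an admission unrelated to knee or device? | Yes, if at the same hospital | Yes, under the all-SAE recording rule |
| Covers the 30-day window? | Collected at the 90-day visit | Events since discharge sought at the 90-day visit |

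On timing, the 90-day visit has a window of ±14 days, so the earliest in-window visit is day 90 − 14 = 76 after implantation. Thirty days after discharge has passed by then unless the index stay exceeded 76 − 30 = 46 days. The existing visit is late enough to ask about the whole window.

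The related adverse events that Appendix C takes from the case report forms do not close the gap. They leave out unrelated admissions, and the plan does not say they feed the readmission rate.

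**2. Illustrative size (assumed inputs, not document figures)**

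Let p be the true rate and f the share of readmissions that go to another hospital, equal in both arms and none recovered.

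- Reported rate = p × (1 − f).
- Reported difference = (pA − pB) × (1 − f).

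For p = 5%:

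- f = 10%: 0.05 × 0.90 = 4.5%
- f = 30%: 0.05 × 0.70 = 3.5%

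For true rates of 6% and 3%, a difference of 3.0 points:

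| f | Reported rates | Difference | Power, 225 per arm |
|---|---|---|---|
| 0 | 6.0% vs 3.0% | 3.0 points | 33.5% |
| 10% | 5.4% vs 2.7% | 2.7 points | 30.6% |
| 20% | 4.8% vs 2.4% | 2.4 points | 27.6% |
| 30% | 4.2% vs 2.1% | 2.1 points | 24.6% |

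With 225 per arm and no loss, 225 × (0.06 + 0.03) = 20.25 readmissions are expected. At f = 30%, 20.25 × 0.30 = 6.1 of them are not counted.

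Power is for a two-sided 5% comparison of two proportions. The figure of 225 is the minimum arm size for the whole study (Section 15). The sub-study is confined to contracted US sites and its size is not given, so the power column shows direction only. Power is low even with complete capture. The main loss is accuracy of the reported rate.

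**The case against.** Bills are a natural source for a cost comparison, and the documents never mention admissions to other hospitals. The primary-outcome line also names hospital data besides the UB forms, and these might include more. This stands as far as it goes: outside admissions can be missed, and the documents do not show that they will be. The undefined hospital data do not remove the point, because readmission is listed expressly under the UB forms and no other source is named for it.

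It also stands that the SAE records are not a complete substitute. Reporting starts when the site discovers the event. The fields of the form are not shown, so an admission date or hospital cannot be confirmed. Section 12's definition of a serious event refers to use of a medical product, which sits awkwardly with its rule to record all such events regardless of relationship. For these reasons the two sources should be combined, and the subject should be asked directly.

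Three stronger readings are tempting but unsupported:

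- **A rate near zero.** Section 11.3 uses the singular for the form, and a reader might infer that only the index bill is collected. Appendix C uses the plural and says the forms will carry readmission information, so later bills from the same hospital appear to be intended.
- **Bias between arms.** Unequal loss would create a spurious difference, for example 0.8 to 2.0 points if 10% were lost in one arm and 30% in the other at equal true rates of 4-10%. But each site is to enrol both arms in alternating series of 10, and the documents give no reason for referral to differ by arm.
- **Conflict with the safety results.** Section 15 summarizes and lists serious events but plans no hospitalization or readmission rate, so there is no competing figure to contradict.

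**Conclusion.** The concern holds in limited form. As written, the 30-day readmission rate rests on the enrolling site's own bills, an admission elsewhere can be recorded as no readmission, and no recovery step is stated. The expected direction is an understated rate in both arms and an attenuated difference.

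The size cannot be determined from the documents. A true 5% reported as 4.5% to 3.5% depends entirely on the assumed 5% rate, the assumed 10-30% share going elsewhere, equal loss in both arms, and no recovery through the undefined hospital data.

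The matter is minor. It affects one listed outcome of an economic sub-study that runs only at contracted US sites. The ALF primary endpoint, KSS, KOOS and the planned safety analyses are not affected. It is still worth correcting, because the change draws mostly on data the trial already requires.

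**What to change.** Amend Appendix C as follows:

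1. Define 30-day readmission as any inpatient admission, at any hospital and for any cause, within 30 days of the index discharge date.
2. Count an admission if it appears in either the SAE records or the UB forms.
3. At the existing 90-day visit, ask each sub-study subject about admissions to other hospitals since discharge, and record the dates.
4. Produce one listing that reconciles the two sources by subject and shows which source identified each admission.
5. Keep the UB forms as the source of billing detail.

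The cost is about one paragraph in Appendix C, one question at a visit already scheduled, and one listing. No new visit is needed. Two limits remain and should be stated with the result: billing detail will be missing for some outside admissions, and capture still depends on the site learning of the event.
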